7.6.1.2. Individual Adverse Events

Analysis population(s): Safety analysis set

Analysis parameter: Adverse events, adverse drug reactions, serious adverse events and reactions, adverse events and reactions leading to discontinuation

Analysis method: For each group, the numbers and proportions of subjects experiencing each type of event will be calculated by event category (solicited adverse events, immediate reactions, other) and by MedDRA/J SOC and PT. Group totals will be shown, as well. Additionally, adverse events and adverse drug reactions will be tabulated by event category (solicited adverse events, immediate reactions, other)

and severity (mild, moderate, severe). If the same subject experiences the same event multiple times at different levels of severity, the event will be tabulated using the highest reported level of severity.

Listings

Listing 7.6.1.2.1: Listing of Adverse Events

Listing 7.6.1.2.2: Listing of Adverse Drug Reactions

7.6.1.3. Incidence of Solicited Adverse Events by Number of Doses

Analysis population(s): Safety analysis set

Analysis parameter: Adverse events and reactions that are considered solicited adverse events

Analysis method: For each number of doses, for each group, and for each MedDRA/J SOC and PT, the numbers and proportions of subjects experiencing each type of event will be tabulated by event category (solicited adverse events, immediate reactions).

7.6.1.4. Adverse Events by Subgroup

7.6.1.4.1 Solicited Adverse Events by Subgroup (Adverse Drug Reactions)

Analysis population(s): Safety analysis set

Analysis parameter: Adverse drug reactions classified as solicited adverse events

Analysis method: For the subgroups shown in Table 7.6.1.4, for each group, the numbers and proportions of subjects experiencing each type of event will be calculated by MedDRA/J SOC and PT.

Table 7.6.1.4: Subgroups

Subgroups	
Sex	Male, Female
Age in months	≥ 2 and < 3 months, ≥ 3 months

7.6.1.4.2 Pyrexia (Solicited Adverse Drug Reactions)

Analysis population(s): Safety analysis set

Analysis parameter: Pyrexia (solicited adverse event) (adverse drug reaction)

Analysis method: For each number of doses, and both overall and by the presence or absence of simultaneous immunization with a pneumococcal vaccine, the number and proportion of subjects experiencing each type of event will be calculated (using the total number of administrated doses as the denominator). The number and proportion of subjects experiencing each type of event will also be calculated by number of injections (1, 2, or 3) and also both overall and by the presence and absence of simultaneous immunization with a pneumococcal vaccine.

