## 8.5 Concomitant Drugs/Therapies

### 8.5.1 Prohibited Concomitant Medication/Therapy

The concomitant use of the following drugs and therapies will be prohibited during the Cohort 1 and 2 study periods (Cohort 1: Visit 1 through Visit 6; Cohort 2: Visit 1 through Visit 4).

- (1) Hib, pertussis, diphtheria, tetanus, or polio vaccines other than the investigational products
- (2) Immunoglobulin preparations
- (3) Corticosteroids at prednisolone equivalent doses of 2 mg/kg/day or higher (except for topical drugs)
- (4) Immunosuppressants (except for topical drugs)
- (5) Blood transfusions
- (6) Immunosuppressant therapies
- (7) Investigational products other than BK1310, ActHIB®, and TETRABIK

The concomitant use of the following drugs will be prohibited from 27 days before until 14 days after the vaccination with investigational product.

(8) Live vaccines (e.g., BCG, measles, rubella, mumps, varicella, rotavirus\*)

\*: Simultaneous vaccination with the investigational product will be permitted only for a rotavirus vaccine

The concomitant use of the following drugs will be prohibited from 6 days before until 14 days after the vaccination with investigational product.

(9) Inactivated vaccines (e.g., Pneumococcal, \*\* influenza, Japanese encephalitis, hepatitis A, hepatitis B\*\*)

\*\*: Simultaneous vaccination with the investigational product will be permitted only for the pneumococcal and hepatitis B vaccines. The site of vaccination will be the thigh or the arm on the opposite side from that used to administer the investigational product.

*Rationale*

- (1) This criterion was established because of the potential effects on the assessments of efficacy.
- (2)(5) These criteria were established because of the potential effects on the assessments of efficacy, since they might contain antibodies to the active ingredients of the investigational drug.
- (3)(4)(6) These criteria were established because of the potential effects on the assessments of efficacy and safety, since these drugs could suppress immune function.
- (7) This criterion was established because of safety and ethics considerations.

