## 4) Causal relationship to the investigational product

For events other than vaccination site reaction, which are pre-specified adverse events, the (sub)investigator will assess whether or not there is a "reasonable possibility" that the investigational product caused the adverse event in question. This assessment is made in consideration of the underlying disease, concomitant medical diseases, and other aspects of the natural course of the primary disease, concomitant therapies risk factors and factors other than the investigational product, and the temporal relationship between investigational product dosing and adverse event onset. If it is unknown or cannot be determined whether or not there is a reasonable possibility, then it will be concluded that there is a reasonable possibility. For all vaccination site reactions (vaccination site redness, swelling, induration, and pain), which are pre-specified adverse events, the causal relationship to the investigational product will be classified as "there is a reasonable possibility." Adverse events for which it is thought "there is a reasonable possibility" of there being a causal relationship with the investigational product are considered adverse drug reactions.

1. Reasonable possibility
2. No reasonable possibility

5) Outcome

The outcomes of adverse events will be classified using the following 6 categories.

1. Recovered
2. Recovering
3. Did not recover
4. Recovered, but with sequelae
5. Death
6. Unknown

6) Day of outcome

The day of outcome will be classified according to the following criteria.

Recovered	: The day of resolution. However, if the day on which the subject recovered cannot be identified, then the day of outcome will be the day on which the outcome was confirmed or determined.
Recovering	: The day on which it was confirmed or determined that the subject was recovering.
Did not recover	: The day on which it was confirmed or determined that the subject had not recovered.
Recovered with sequelae	: The day on which it was confirmed or determined that sequelae were present.
Death	: The day of death. However, if the day of death cannot be determined, then this will be the day on which the death was confirmed or determined.
Unknown	: The day of death if the subject died due to a cause other than the adverse event in question and the outcome was unknown. Otherwise, this will be the day on which the outcome was confirmed or determined.

7) Follow-up Investigation

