2.5. Sample Size Justification

○ Target sample size

Cohort 2: 340 subjects (BK1310 L group or H group: 170 subjects; control group: 170 subjects)

Rationale

Cohort 2 is positioned as a cohort for exploring the seroprotection rate in a phase 3 confirmatory study, and it was therefore decided that a sample size of 340 subjects (170 subjects per group) would allow for a proper assessment, taking into account the precision of estimating anti-PRP antibodies, etc.

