11. OUTPUT LISTINGS

Table Number	Contents
Table 7.2.1	Eligibility for Analysis Sets (Randomized Subjects)
Table 7.2.2	Disposition of Subjects and Discontinued Subjects (Randomized Subjects)
Table 7.3.1	Demographics and Other Baseline Characteristics (FAS)
Table 7.3.2	Demographic and Other Baseline Characteristics (Safety Analysis Set)
Table 7.4	Status of Immunization With Investigational Product by Number of Doses (Safety Analysis Set)
Table 7.5.1	Antibody Seroprotection Rate at 4 Weeks After the Primary Immunization (FAS)
Table 7.5.2.1	Anti-PRP Antibody Seroprotection Rate at Concentrations $\geq 0.15 \mu\text{g/mL}$ at 4 Weeks After the Primary Immunization (FAS)
Table 7.5.2.2	Antibody Titer Time Profiles (FAS)
Table 7.5.3.4	Antibody Titer Time Profiles by Site (FAS)
Table 7.5.3.8.1	Antibody Seroprotection Rate by Subgroup (FAS)
Table 7.5.3.8	Antibody Titer Time Profiles by Subgroup (FAS)
Table 7.6.1.1	Summary of Adverse Events and Adverse Drug Reactions (Safety Analysis Set)
Table 7.6.1.2.1.1	Disposition of Adverse Events (Safety Analysis Set)
Table 7.6.1.2.1.2	Disposition of Adverse Drug Reactions (Safety Analysis Set)
Table 7.6.1.2.1.3	Disposition of Serious Adverse Events (Safety Analysis Set)
Table 7.6.1.2.1.4	Disposition of Serious Adverse Drug Reactions (Safety Analysis Set)
Table 7.6.1.2.1.5	Disposition of Adverse Events Leading to Discontinuation (Safety Analysis Set)
Table 7.6.1.2.1.6	Disposition of Adverse Drug Reactions Leading to Discontinuation (Safety Analysis Set)
Table 7.6.1.2.2.1	Disposition of Adverse Events by Severity (Safety Analysis Set)
Table 7.6.1.2.2.2	Disposition of Adverse Drug Reactions by Severity (Safety Analysis Set)
Table 7.6.1.3.1	Solicited Adverse Events by Number of Doses (Safety Analysis Set)
Table 7.6.1.3.2	Solicited Adverse Events by Number of Doses (Adverse Drug Reactions) (Safety Analysis Set)
Table 7.6.1.4.1	Solicited Adverse Events by Subgroup (Adverse Drug Reactions) (Safety Analysis Set)
Table 7.6.1.4.2	Emergence of Pyrexia by Subgroup (Adverse Drug Reactions) (Safety Analysis Set)

Listing 7.2.2	Listing of Discontinuations (Discontinued Subjects)
Listing 7.3.1	Listing of Subject Backgrounds (Randomized Subjects)
Listing 7.3.2	Listing of Concomitant Medications (Randomized Subjects)
Listing 7.4	Listing of Doses of Investigational Product (Safety Analysis Set)
Listing 7.5.2.2	Antibody Titer Listing (FAS)
Listing 7.6.1.2.1	Listing of Adverse Events (Safety Analysis Set)

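### In the Cohort 2 SAP, the only table of pyrexia by simultaneous pneumococcal vaccination counts just pyrexia judged related to the study product, which can distort the with/without contrast.

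*SAP*

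**What the plan says.** Protocol 8.5.1 allows some vaccines on the same day as the study product. For inactivated vaccines it says: "Simultaneous vaccination with the investigational product will be permitted only for the pneumococcal and hepatitis B vaccines". Rotavirus vaccine is also allowed on the same day. Simultaneous vaccinations are recorded (Protocol 9.2.2).

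Cohort 2 SAP 7.6.1.4.2 tabulates pyrexia "both overall and by the presence or absence of simultaneous immunization with a pneumococcal vaccine", first "using the total number of administrated doses as the denominator" and then by injection number (1, 2 or 3). The parameter is "Pyrexia (solicited adverse event) (adverse drug reaction". The section heading carries the same restriction, and so does the table title in SAP section 11: "Emergence of Pyrexia by Subgroup (Adverse Drug Reactions) (Safety Analysis Set". It is therefore deliberate and not a slip in one line.

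An adverse drug reaction is an adverse event with a reasonable possibility of being caused by the investigational product (SAP 4.2(3)). Protocol 9.2.4.2 classes all solicited vaccination site reactions as related by rule. Pyrexia is a systemic reaction, so the (sub)investigator judges it individually, weighing among other things "concomitant therapies risk factors and factors other than the investigational product". If the relationship is unknown or cannot be determined, the event is classed as related.

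**The concern.** A table meant to show how fever varies with co-vaccination should define fever in the same way in both strata. Here a fever is counted only if the assessor does not rule out the study product, and one of the things the assessor weighs is concomitant treatment. The observer blind in Protocol 5.3.1.3 covers the study product; nothing described hides pneumococcal status. The assessor can therefore know the stratum when making the judgement that decides whether the fever is counted. A fever can be attributed to the pneumococcal vaccine, and dropped for that reason, only in the co-vaccinated stratum.

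No other planned output fills the gap. SAP 7.6.1.3 tabulates solicited events regardless of causality by dose and group, but not by pneumococcal status. SAP 7.6.1.4.1 covers sex and age subgroups only, and again only adverse drug reactions. At stake is whether a reader of this one table can tell a real absence of extra fever from one produced by attribution.

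**Working it through.** The plan gives no pyrexia rate, no share of doses given with pneumococcal vaccine and no share of fevers judged related, so there is no figure to reproduce. What follows shows only how the filter acts.

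**From the documents.** The Cohort 2 target is given as "Cohort 2: 340 subjects (BK1310 L group or H group: 170 subjects; control group: 170 subjects". With three doses each, the dose denominator is at most 340 × 3 = 1,020.

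**Assumed.** All-cause pyrexia per dose: pN = 10% without and pC = 20% with pneumococcal vaccine. Shares judged related: qN and qC, between 50% and 100%.

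**Formulas.**
- All-cause difference = pC − pN = 20 − 10 = 10 points; ratio = 20/10 = 2.0.
- Difference in the planned table = pC·qC − pN·qN.
- Ratio in the planned table = (pC/pN) × (qC/qN).

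The ratio is understated when qC is below qN. The difference is understated when pC(1 − qC) exceeds pN(1 − qN), that is, when more points of fever are dropped from the co-vaccinated stratum than from the other.

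| qN | qC | Without | With | Difference (points) | Ratio |
|---|---|---|---|---|---|
| 100% | 100% | 10% | 20% | 10 | 2.0 |
| 90% | 90% | 9% | 18% | 9 | 2.0 |
| 90% | 80% | 9% | 16% | 7 | 1.78 |
| 90% | 70% | 9% | 14% | 5 | 1.56 |
| 90% | 50% | 9% | 10% | 1 | 1.11 |
| 70% | 90% | 7% | 18% | 11 | 2.57 |

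If instead 5 points of unrelated background fever are removed from each stratum, the rates become 5% and 15%. The difference stays at 10 points and the ratio rises to 3.0.

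**Other assumed rates, with qN = 90% and qC = 70%.**
- 10% and 30%: the table shows 21 − 9 = 12 points against a true 20, and a ratio of 2.33 against 3.0.
- 20% and 40%: the table shows 28 − 18 = 10 points against a true 20, and a ratio of 1.56 against 2.0.

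The contrast can thus shrink, stay the same or grow, according to attribution shares that the documents do not give. Counting all solicited pyrexia sets qN = qC = 100% and removes the dependence.

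**The case against.** The strongest reply is the causality rule itself. The threshold is low, and undeterminable cases count as related. When two vaccines are given on the same day, attributing a fever partly to the pneumococcal vaccine is not enough to drop it; the assessor must find no reasonable possibility that the study product contributed. If assessors apply the default to every fever, there is no bias. This stands as a limit on the size. It does not remove the problem, because the default applies only when the assessor cannot decide.

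A reader might infer that the table certainly understates the effect because fevers are lost from one stratum only. The documents do not support that. Assessors also weigh underlying and concomitant illness, which can remove fevers from either stratum. Infants without pneumococcal vaccine may still have had hepatitis B or rotavirus vaccine that day.

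A reader might also infer that the table pools BK1310 with control, since 7.6.1.4.2 lacks the by-group wording of 7.6.1.4.1 ("For the subgroups shown in Table 7.6.1.4, for each group, the numbers and proportions of subjects experiencing each type of event"). Protocol 13.3.3 requires adverse events and adverse drug reactions to be calculated by vaccination group, and SAP section 9 records no departure from the protocol. The phrase is missing and should be added; pooling is not what the plan says.

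Finally, the study objective is BK1310 against control, no significance level is set, and the table is descriptive. All of that stands and limits the importance of the point. The underlying data could support an all-cause table later, but none is planned.

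**Conclusion.** The point holds in a limited form. The only planned look at pyrexia by pneumococcal co-vaccination uses an outcome filtered by a case-by-case judgement that can depend on co-vaccination. Understatement is the most plausible direction, since only co-vaccinated infants can have a fever attributed to the pneumococcal vaccine. Direction and size nevertheless rest on unknown attribution shares. The range of 1 to 11 points around a true 10 depends wholly on assumed rates, and the bias could be nil.

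The consequence is confined to one exploratory safety table with a non-randomised stratifier. The change is worth making because it is cheap and the unfiltered outcome is objectively defined.

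**What to change.** In Cohort 2 SAP 7.6.1.4.2:

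- Tabulate all solicited pyrexia (axillary temperature of 37.5 °C or more, up through Day 14) regardless of causality, by dose and pneumococcal status.
- Keep the adverse-drug-reaction version alongside it.
- State explicitly that the tabulation is for each group (H and control), as in 7.6.1.4.1 and in line with Protocol 13.3.3.
- Rename Table 7.6.1.4.2 in section 11 to match.

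The cost is SAP wording and one more descriptive table. Protocol 9.2.4.1 already has axillary temperature entered daily in the e-Diary, and 9.2.2 already has simultaneous vaccination recorded, so no new procedure is needed. The downside is that all-cause counts will include some unrelated febrile illness, which is a reason to show both versions. The change does not make co-vaccination randomised, so the table should still be read as descriptive.

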### 9.2.2 Vaccination Status

The (sub)investigator or a clinical research coordinator will record the following information in the case report form.

- (1) Drug number
- (2) Day of vaccination with investigational product
- (3) Body temperature (axillary) prior to vaccination with the investigational product
- (4) Site of vaccination with the investigational product
- (5) Status of simultaneous immunization with a vaccine other than the investigational product (day of vaccination, type of vaccine simultaneously administered, site of vaccination)

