### 9.2.4.2 Adverse Events

An adverse event is any clinically undesirable or unintended sign (including clinically significant test value abnormalities), symptom, or disease that occurs during the safety assessment period following vaccination with the investigational product, regardless of whether or not it is causally related to the investigational product.

Furthermore, vaccination site reactions (redness, swelling, induration, pain) and systemic reactions (pyrexia, irritability, crying, decreased appetite, decreased sleep, increased sleep), which are reactions that are specific to vaccination, that occur in the period up through Day 14 after vaccination with the investigational product will be considered pre-specified adverse events. Vaccination site reactions to other

vaccines that were administered at the same time will be considered normal adverse events, and will not be considered pre-specified adverse events. Axillary body temperature  $\geq 37.5^{\circ}\text{C}$  will be handled as the adverse event “pyrexia.” In addition, adverse events that occur within 30 minutes after vaccination with the investigational product will be considered immediate reactions.

(1) Symptoms or diseases

The (sub)investigator will confirm the presence or absence of adverse events based on the contents of the e-Diary that has been filled out by the legal guardian, as well as by questioning of the legal guardian and observation of the subject.

(2) Clinical laboratory test abnormalities

The (sub)investigator will handle as an adverse event any event that is judged to be a clinically significant abnormality.\*

\*: A “clinically significant test value abnormality” will be determined based on the following criteria.

- When there is a relationship to a clinical sign or symptom

However, if these symptoms or signs have been reported as separate adverse events, then there is no need to handle this test value abnormality as an adverse event.

- When a medical or surgical treatment has been administered for the test value abnormality in this clinical laboratory tests
- When the investigational product vaccination method has been changed (e.g., a change in the dose, treatment interruption, treatment discontinuation) because of the test value abnormality
- When the (sub)investigator determines for some other reason that the finding is a clinically significant abnormality

(3) Safety assessment period

1) Cohort 1

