6.4.2. Handling Period of Adverse Event Data by Number of Injections

Adverse events to be summarized as the number of applicable vaccinations are those that occur after the vaccination on the day of the vaccination in question and before the vaccination on the day of the next vaccination. For the fourth vaccination, adverse events that occurred from the day of the fourth vaccination to the last day of the safety assessment period will be summarized.

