- Control group: Subjects will receive 0.5 mL of each of ActHIB and Tetrabik

For the primary immunization,* subjects will receive 3 subcutaneous doses (as a rule, administered at the top part of the upper arm extensor) at intervals of 3 to 8 weeks (standard vaccination interval: 4 weeks). Subjects in the control group will receive subcutaneous doses of Tetrabik and ActHIB (as a rule, administered at the top and bottom, respectively, of the upper arm extensor on the same side). However, the repeated vaccination with investigational product at the same location as that which was used for the previous dose will be avoided.

*: The completion of the primary immunization series with the investigational product. For the booster immunization, a dose will be administered as part of, for example, routine immunization.

(3) Cohort 3

Only for subjects from whom written informed consent has been obtained, after the end of Cohort 2, and generally after 4 weeks have passed since the administration of the booster immunization received as part of, for example, routine immunization, the investigator will perform antibody titer measurements as a follow-up investigation, depending on the results that have been obtained after the primary immunization in Cohort 2, or in accordance with the wishes of the subject (subject's legal guardian).

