6.3. Handling of Antibody Titer Data Below the Limit of Quantitation

For the calculation of the descriptive statistics, if the measured antibody titer is below the limit of quantitation, then it will be treated as being the lower limit of quantitation divided by 2.

6.4. Handling of Adverse Event Data When There Are Multiple Events In the Same Period

If the same PT occurs in the same subject occurs multiple times in the period in question (e.g., the safety assessment period or the specified period for each number of doses), then these will only be counted as a single event.

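### Cohort 2 SAP, Section 7.6.1.4.2: the first pyrexia tabulation puts subjects over doses, so any row that pools doses and counts each child once is neither a per-subject nor a per-dose incidence (minor)

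*SAP*

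**What the plan says.** Section 7.6.1.4.2 of the Cohort 2 SAP sets two tabulations of solicited pyrexia classed as an adverse drug reaction.

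- **First tabulation.** It opens "For each number of doses, and both overall and by the presence or absence of simultaneous immunization with a pneumococcal vaccine" and continues: "the number and proportion of subjects experiencing each type of event will be calculated (using the total number of administrated doses as the denominator".
- **Second tabulation.** The number and proportion of subjects "will also be calculated by number of injections (1, 2, or 3"), with the same split by pneumococcal co-vaccination. No dose denominator is given here.

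Section 6.4 of the same SAP counts a preferred term once per subject within "the period in question (e.g., the safety assessment period or the specified period for each number of doses"). It does not say which of those two periods applies to the pyrexia table.

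No passage states that the first numerator is febrile doses, or that a child may be counted more than once.

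**The concern.** A proportion should have the same unit above and below the line. Here the stated numerator is children and the stated denominator is doses. When several doses are added together, a child who is febrile after all three adds one to the top and three to the bottom.

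The resulting percentage would not tell a reader how many children had fever, nor how often a dose was followed by fever. It would sit below the per-dose incidence whenever any child was febrile more than once. Two programmers working from this text could also produce different tables. What is at stake is the accuracy of one reported fever figure, not an efficacy result.

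**Working it through.** **Which rows are exposed.** The text allows three readings:

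| Reading | Numerator | Denominator | Units agree? |
|---|---|---|---|
| (a) Rows within one dose number | children febrile after that dose | doses given at that number, i.e. children dosed | yes |
| (b) Doses pooled, child counted at each febrile dose | febrile dose occasions | dose occasions | yes |
| (c) Doses pooled, child counted once | children febrile at least once | dose occasions | no |

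Two features favour pooling, (b) or (c), over (a). First, the second tabulation already gives results by injection 1, 2 or 3 with the same pneumococcal split, so a per-dose first tabulation would repeat it. Second, a total of administered doses suggests a sum; within one dose number it would simply be the number of children dosed. Section 7.6.1.3, which is a by-dose table, specifies no dose denominator.

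Between (b) and (c), the literal word is subjects, and Section 6.4 permits the whole safety period as the counting period, which gives (c). It equally permits the period for each dose, which gives (b).

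**Inputs for the size under (c).** Group size is 170 (Cohort 2 SAP, Section 2.5) and there are 3 doses per child (Protocol, Section 8.4). The documents give no pyrexia rate, so the per-dose risk *p* is assumed over a range, with doses taken as independent.

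**Ceiling, row over all doses.** 170 × 3 = 510 doses. If every child is febrile at least once, the figure is 170/510 = 33.3%. It depends only on three doses per child, so it is the same with both groups combined (340/1,020).

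**Formulas.** Per-dose incidence = *p*. Per-subject incidence = 1 − (1 − *p*)³. Literal figure under (c) = [1 − (1 − *p*)³]/3.

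| Assumed *p* (per-dose incidence) | Per-subject incidence | Literal figure under (c) |
|---|---|---|
| 5% | 14.3% | 4.8% |
| 10% | 27.1% | 9.0% |
| 20% | 48.8% | 16.3% |
| 30% | 65.7% | 21.9% |
| 40% | 78.4% | 26.1% |

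In counts at 20%: 0.20 × 510 = 102 febrile dose occasions, and 0.488 × 170 ≈ 83 children febrile at least once. The three candidate figures are 102/510 = 20%, 83/170 = 48.8% and 83/510 = 16.3%.

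**Can each pyrexia be tied to one dose?** Yes. Protocol Section 9.2.4.2 limits pre-specified reactions to those "that occur in the period up through Day 14 after vaccination with the investigational product will be considered pre-specified adverse events". Doses are given "at intervals of 3 to 8 weeks (standard vaccination interval: 4 weeks"). With vaccination as Day 1, the next dose falls no earlier than Day 1 + 21 = Day 22, so the solicited windows do not overlap. Co-vaccination is recorded as part of vaccination status (Protocol, Section 9.2.2): "Status of simultaneous immunization with a vaccine other than the investigational product (day of vaccination, type of vaccine simultaneously administered, site of vaccination"). A dose-level table therefore needs no new data.

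**The case against.** The strongest reply is that only reading (c) fails, and that it is the least likely to have been meant. A dose denominator is itself a signal that the table is at dose level. Section 6.4 names the period for each dose as an option. The duplication argument shows that doses are pooled, but it supports (b) as well as (c). Moreover, the sentence opens as Section 7.6.1.3 does, which leaves (a) possible, and the word overall may mean only regardless of pneumococcal status. Most of this stands: pooling is an inference, and (b) was probably intended. It does not remove the point, because the numerator as written is subjects and nothing in the Cohort 2 SAP redefines it.

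It also stands that the sizes rest on assumed rates. At 10% the gap is about one percentage point (9.0% against 10%), and the ceiling is reached only if every child is febrile at least once.

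A reader might infer more than the documents support in two ways:

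- **That fevers cannot be assigned to doses.** The Cohort 1 SAP, Section 6.4.2, assigns the following events to a dose: "those that occur after the vaccination on the day of the vaccination in question and before the vaccination on the day of the next vaccination". The Cohort 2 SAP has no such clause. For this table the omission changes nothing, because the Day 14 limit and the minimum three-week spacing already link each solicited pyrexia to one dose.
- **That the trial's account of fever is unreliable.** It is not. Adverse events are tabulated by subject and group in Section 7.6.1.2, solicited events by dose and group in Section 7.6.1.3, and pyrexia by injection number and pneumococcal status in the second sentence of Section 7.6.1.4.2. None of these has the mismatch.

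**Conclusion.** Wrong as written, and minor. The mismatch arises only if the rows pool doses, which is the more plausible reading, and each child is counted once, which Section 6.4 allows but does not require. On that combination the figure over all doses cannot exceed 33.3% with three doses per child, and it would be 16.3% where the per-dose incidence is 20%. The second number assumes the 20% risk, independence between doses and full dosing. Under either of the other two readings nothing is wrong.

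The effect is confined to one descriptive safety table in an exploratory cohort, with no test or confidence interval specified for it. No study conclusion depends on it.

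**What to change.** In Section 7.6.1.4.2 of the Cohort 2 SAP:

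1. For rows that pool doses, define the proportion as the number of dose occasions followed by solicited pyrexia (at most one per dose occasion) divided by the number of dose occasions in that stratum. Subjects over subjects dosed would also be consistent in the overall row. The dose-level form suits the pneumococcal split better, since one child may be co-vaccinated at one dose and not at another.
2. State that the Section 6.4 counting period for this table is the period for each dose.
3. Keep subjects over subjects dosed for the rows by injection number.

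Carrying over Section 6.4.2 from the Cohort 1 SAP is not needed for this table. The cost is a sentence or two and a small change to one table program, with no new data.
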